8.3 Interviewer Safety

The following measures will be taken to ensure interviewer safety:

- The majority of interviews will be conducted remotely (phone or video call).
- Researchers will always inform their line manager, the PI or the trial manager of their interview schedule and whereabouts, including informing them when the interview is complete.
- If interviews are being conducted in-person, researchers will only interview male participants in PDU/JSWT.
- Similarly, researchers will interview female participants in rooms in services, women's support services, libraries or children's centres.
- Researchers will never interview participants in the participant's home.
- A work mobile number rather than a personal mobile number will be given to potential participants.
 While interviews will be conducted using Microsoft Teams, calls and text message reminders will be sent to participants throughout the trial.
- Debriefing/supervision for the researcher will be available from their line manager.
- Clinical debriefing will be provided to all researchers.
- When interviewing from home using video calling, researchers are advised to blur their background and ensure there is nothing that could identify where they live.

Telephone interviews will be scheduled within normal working times (where possible) when researchers have access to discussing safeguarding issues with staff at the substance use treatment service and/or the

ADVANCE-D clinical lead. If interviews are conducted after office hours, researchers will ensure access to the ADVANCE-D clinical lead is organised.

9. ETHICS APPROVAL

This protocol and related documents will be submitted for review to the Integrated Research Application Service (IRAS Project ID 328020) and the study has been approved by His Majesty's Prison and Probation Service (HMPPS) National Research Committee (NRC Reference 2023-262) and by NHS West of Scotland Research Ethics Service (REC 24/WS/0068).

9.1 PROTOCOL AMENDMENTS AND VERSION CONTROL OF STUDY DOCUMENTS

The Trial Manager will be responsible for preparing and submitting protocol amendments to the ethics committees. The Trial Manager will be responsible for updating the ISRCTN register subsequent to relevant protocol amendments.

10. STATISTICAL METHODS

A senior statistician will oversee the analysis conducted by the trial statistician performed using Stata version 18 (or later). A detailed statistical analysis plan (SAP) drafted by a Statistician following KCTU Standard Operating Procedures blinded to any outcome data and agreed with the TSC prior to assessing outcome data will ensure the study is conducted according to CONSORT guidelines.⁸⁴

The estimand framework will be described in full in the SAP and will cover the population, endpoint (ABI-Total Score), treatment condition (comparison of ADVANCE-D versus usual CJOM), intercurrent events (such as: suicide, all-cause mortality (non-suicide), returning to prison, and population summarise (adjusted mean difference). Rationale for the estimand is to describe the comparison between ADVANCE-D versus usual CJOM under routine practice.

10.1 PRIMARY OUTCOME

1. (Adapted) Abusive Behavior Inventory (ABI) total score at 12 months⁶⁷

10.2 SECONDARY OUTCOMES

1. IPV perpetration/victimisation (eight domains)

(Adapted) Revised Abusive Behavior Inventory (ABI-R) (women only);⁶⁹

(Adapted) Revised Controlling Behaviors Scale (CBS-R);⁷⁰

Technology facilitated abuse;⁷¹

Locked in;

Stalking/Harassment;

Using Children against partner;⁷²

Feeling of safety;⁷² (women only)

(Adapted) Intimate Partner Violence Responsibility Attribution Scale (IPVRAS) (men only) $^{101}\,$

2. Substance use

Treatment Outcomes Profile (partial - total alcohol and drug free days in past 28 days);⁷³ Alcohol Use Disorder Identification Test (AUDIT) total score in the past 12 months at 12 months follow-up;⁷⁴

Drug Use Disorder Identification Test (DUDIT) total score in the past 12 months at 12 months follow-up 75

3. Well-being

Depression symptoms (PHQ-9);⁷⁶ Generalised Anxiety Disorder symptoms (GAD-7);⁷⁷ Primary Care PTSD (PC-PTSD-5);⁷⁸

Propensity for Abusiveness Scale (PAS) [anger subscale]⁷⁹ (men only)

4. Self-control: Brief Self-Control Scale (BSCS)⁸⁰ (men only)

5. Children's well-being⁷²

6. Quality of Life: EQ-5D-5L⁸¹

10.3 SAMPLE SIZE JUSTIFICATION

To detect an effect size of 0.4,^{85,86} with 90% power and 5% significance (2-sided), a sample of 266 is required for an individually randomised trial. To inflate to a cluster RCT design, by randomising 26 PDU/JSWT with an average cluster size of 13.5 and an ICC=0.03,⁸⁷ the number analysed is inflated to 358. To account for 18% drop out of both offenders³⁷ and PDU/ JSWT we will plan to randomise 32 PDU/ JSWT (1:1) and enrol 450 offenders (14 per PDU/ JSWT).

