A solution to the need for perpetrator interventions in probation that are responsive to substance misuse, is the bespoke ADVANCE integrated perpetrator programme for heterosexual men who misuse substances and are abusive towards a female (ex)-partner. ADVANCE was originally developed and tested for men in substance misuse treatment⁴⁶ as part of a NIHR Programme Grant (RP-PG-1214-20009) and has been offered to 94 men (54 in the treatment arm of a RCT and 40 in a feasibility study). 47,48 We found it was feasible for trained substance misuse treatment staff to deliver and acceptable to men on the programme. Men offered the ADVANCE group intervention, compared to usual substance misuse treatment only, reported promising clinical outcomes and positive behaviour change, including reductions in IPV. 47,49 In 2020-21, ADVANCE was adapted for digitally-supported delivery (ADVANCE-D) and piloted with 40 men in substance misuse treatment during Covid-19 restrictions. 48 At the end of the 16-week intervention: 68% of the 25 men followed-up reported reductions in IPV (physical, sexual or psychological) perpetration (73% of the 11 (ex)-partners followed-up reported reductions in experiencing IPV), 40% of men reported reductions in controlling behaviours (46% of their (ex)-female partners reported a reduction in experiencing controlling behaviours). Women also reported reductions in men using their children against them. Some women reported positive behaviour changes in their partner from attending the programme: "He'd normally hold everything and then throw it in my face in an argument, but now we're having conversations about it". Women valued the linked support stating: "To be able to say that I do feel scared sometimes. To know there is somebody who can check up and ... ask if I feel okay ... feels like I have back up" Facilitators also reported behaviour change among men in the group: "By the end of it, they were completely able to identify with behaviours... (and) reflect on the positive influence it had on their relationships...". The content of ADVANCE-D was well-received by both men and facilitators. Men rated the sessions highly and understood the aims of each session. Some men preferred digital over in-person sessions as they offered increased

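### Section 10.3 claims to cover 18% loss of both men and clusters at 90% power, but the allowance is applied once; with both losses unadjusted power is about 85%

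*Protocol*

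**What the plan says.** The whole calculation is in one paragraph of the protocol, section 10.3 (Sample size justification).

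- Individual-level requirement: "To detect an effect size of 0.4", "with 90% power and 5% significance (2-sided), a sample of 266 is required for an individually randomised trial".
- Inflation for clustering: "by randomising 26 PDU/JSWT with an average cluster size of 13.5 and an ICC=0.03", after which "the number analysed is inflated to 358".
- Allowance for loss: "To account for 18% drop out of both offenders" and of PDU/JSWT, "we will plan to randomise 32 PDU/ JSWT (1:1) and enrol 450 offenders (14 per PDU/ JSWT").

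The paragraph does not say whether the two 18% losses are one overall loss or act one on top of the other. The synopsis repeats only the 450 men and 32 units.

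**The concern.** The sentence on loss names two units, men and clusters, and attaches 18% to both. A funder, steering committee or DMC would take it that the trial keeps 90% power if 18% of units drop out and 18% of the men in the remaining units are also lost. Losses at two levels multiply: the fraction retained is 0.82 x 0.82 = 0.672, a total loss of 32.8%. The step from 358 analysed to 450 enrolled allows a total loss of only 1 - 358/450 = 20.4%. The design therefore cannot have the property the sentence gives it if the losses are cumulative. At stake is the stated power, which is the basis for the recruitment target and the yardstick for judging attrition during the trial.

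**Working it through.** **Inputs, all from section 10.3:** effect size d = 0.4; two-sided 5%; 90% power; 266 men if individually randomised; 26 clusters analysed; average size m = 13.5; ICC = 0.03; 358 analysed; 18% loss; 32 clusters and 450 men enrolled, 14 per cluster.

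**1. The individual-level figure reproduces.** A two-sample t calculation gives 133 per arm, 266 in total. The normal approximation gives 264.

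**2. Inflation for clustering.** Design effect = 1 + (m - 1) x ICC = 1 + 12.5 x 0.03 = 1.375.
- 266 x 1.375 = 365.75, so 366.
- 26 x 13.5 = 351.
- Stated: 358, which is 2.2% below 366.

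358 would follow from m of about 12.5 (266 x 1.345 = 357.8). Power at 358 with m = 13.5 is 89.7% (normal).

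**3. Where the 18% goes.**
- Clusters: 26 / 0.82 = 31.7, rounded up to 32; in reverse, 32 x 0.82 = 26.2. The step from 26 to 32 uses the whole allowance.
- Men within retained clusters: 1 - 13.5/14 = 3.6%.

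**4. Number analysed if both losses occur.**
- 26 x 14 x 0.82 = 298, or 11.48 per cluster.
- 450 x 0.82 x 0.82 = 303, taken at 450 x 0.82 / 32 = 11.53 per cluster.

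**5. Power.** Effective N = N / design effect, and normal power = Phi(0.4 x sqrt(effective N / 4) - 1.96). For 298 men the design effect is 1 + 10.48 x 0.03 = 1.314, the effective N is 227, and power = Phi(3.014 - 1.96) = 85.4%. The t column uses a noncentral t with (clusters - 2) degrees of freedom.

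| Scenario | Men analysed | Clusters | Normal | t, clusters - 2 df |
|---|---|---|---|---|
| As stated, m = 13.5 | 358 | 26 | 89.7% | 87.2% |
| 18% of men lost, no clusters | 369 | 32 | 91.8% | 90.0% |
| 18% of clusters lost, no men | 364 | 26 | 89.9% | 87.4% |
| Both, from 26 x 14 x 0.82 | 298 | 26 | 85.4% | 82.4% |
| Both, from 450 x 0.82 x 0.82 | 303 | 26 | 85.8% | 82.9% |

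The 266 in section 10.3 comes from a t reference on N - 2 degrees of freedom. On that basis the two bottom rows are 85.2% and 85.6%, so it hardly differs from the normal column.

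**The case against.** The best defence is that one overall 18% loss was meant, expressed once in clusters and once in men. On that reading the plan works: 26/0.82 = 31.7 gives 32 clusters, 358/0.82 = 437 is within 450, and 450 x 0.82 = 369 exceeds both 358 and 366. This stands as a possible intention. It does not rescue the sentence, which never says the losses are alternatives and which readers will take as protection against both.

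A second defence is that the power figures are unadjusted. The primary model in section 10.4.1 adjusts for baseline ABI, uses the 4- and 12-month assessments, and includes men seen at either time-point. This too stands in part. Suppose adjustment multiplies the variance by 1 - r^2, where r is the correlation between baseline and 12-month ABI. Then r = 0.4 to 0.5 would bring the 298-man scenario to 91-94% (normal) or 88-92% (t, 24 df). The protocol gives no such correlation and section 10.3 claims no gain from adjustment, so r is an assumption here and the recovery is not established.

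Three stronger readings are tempting and not supported:

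- *That 358 is an error for 366 which undermines the target.* The three figures disagree, but 13.5 is an average and may be rounded, so the text does not show which number is off. Also 366/0.82 is about 447, still within 450.
- *That power is simply 82%.* The lower figures need a t reference on cluster degrees of freedom, a stricter convention than the one that produced 266.
- *That pilot follow-up shows worse loss is coming.* Section 1.1 reports 40 men piloted and "68% of the 25 men followed-up reported reductions in IPV", so 25/40 = 62.5% were followed up. Those men were in substance misuse treatment during Covid-19 restrictions. Follow-up that low would also fall in the stop band of section 10.6 (64% or below).

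**Conclusion.** The point holds as a mismatch between the stated allowance and the figures behind it. The plan covers one 18% loss. If men and clusters are both lost at that rate, about 298 to 303 men in 26 clusters are analysed rather than 358. Power falls from the stated 90% to about 85-86% on a convention close to the protocol's own, or 82-83% with a t reference on 24 degrees of freedom. This rests on d = 0.4, ICC = 0.03, equal cluster sizes, no covariate adjustment, and reading the two losses as cumulative.

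The disagreement between 351, 358 and 366 is a minor inconsistency that does not carry the finding. A reader might infer that the trial is too small. The documents do not show that: under one overall loss the target is adequate, and under both losses the shortfall is 4 to 5 points before any gain from adjustment.

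**What to change.** Reword the loss sentence in section 10.3 in one of two ways.

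- **(a) One overall loss.** State that 18% is a single, non-cumulative allowance: 450 x 0.82 = 369 men analysed. Give power as about 90-92% by normal approximation, or about 87-90% by t on cluster degrees of freedom. The lower end of each range applies if whole clusters are lost and the upper end if only men are lost.
- **(b) Both losses.** Keep the present meaning and state about 300 men analysed in 26 clusters, with about 85% power before covariate adjustment.

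In the same edit, make the analysed number agree with its inputs: 266 x 1.375 = 366 or 26 x 13.5 = 351, against 358 as stated. Either the average size or the total should change.

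The cost is a few lines in section 10.3 and, under (b), a lower stated power. No extra recruitment, no change to the analysis and no change to the synopsis is needed, since the synopsis gives only 450 men and 32 units.

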10.4 STATISTICAL METHODS FOR PRIMARY AND SECONDARY OUTCOMES

10.4.1 STATISTICAL METHODS FOR PRIMARY OUTCOME

We will analyse the primary outcome using multi-level linear regression model, including assessments at 4 and 12 months to assess the difference in ADVANCE-D and control at 12-months (primary assessment time-point). Participants and PDU/JSWT will be fit as random effects, and pre-specified fixed effects for participant age, baseline IPV severity, and baseline ABI total score, and region. The adjusted mean difference (aMD) in the Abusive Behavior Inventory (ABI) total score between those from ADVANCE-D with CJOM compared to Usual CJOM will be presented with the associated two-sided confidence intervals (95% CI) and p-value, and intraclass correlation coefficient (ICC). The analysis will use the ITT population that will include all participants who were followed up at either the 4- or 12-month time-point. Pattern missingness will explore the missing data. A CACE will be developed as a sensitivity analysis to the primary analysis. Sensitivity analyses will be used for modelling the different intercurrent events. An additional sensitivity analysis will use the partner IPV data.

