5. ASSIGNMENT OF INTERVENTIONS

5.1 RANDOMISATION METHOD

To reduce selection and recruitment bias, PDU/JSWTs will be randomly allocated to experimental or control arms in a 1:1 ratio to deliver ADVANCE-D+CJOM or usual CJOM. The sequence will be generated by the King's Clinical Trials Unit (KCTU)-affiliated statistician, using block covariate minimisation at the cluster level developed by Carter and Hood.⁶⁶ The following covariates will be used for the clusters: % non-white ethnicity, size of unit/team, index of multiple deprivation (IMD) by decile^a and classification of region (urban/rural)^b. Cluster allocation will then be communicated to the trial manager, who will then inform the PDU/JSWT. PDU/ JSWT make decisions on the CJOM required to address any treatment/support recommended by court.

^aIMD data obtained from:

England: https://imd-by-postcode.opendatacommunities.org/imd/2019

Scotland: https://www.gov.scot/publications/scottish-index-of-multiple-deprivation-2020v2-postcode-look-up/

^bClassification of region data obtained from:

England: https://www.nomisweb.co.uk/sources/census 2021 pc

Scotland: https://www.gov.scot/publications/scottish-government-urban-rural-classification-2020/pages/1/

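### At least three of the four factors used to minimise clusters are missing from the primary model, and its region term is undefined; to the extent those factors are prognostic, the standard error is somewhat too large

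*Protocol*

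**What the plan says.** Protocol 5.1 states that units are "randomly allocated to experimental or control arms in a 1:1 ratio", "using block covariate minimisation at the cluster level". It names the factors: "The following covariates will be used for the clusters: % non-white ethnicity, size of unit/team, index of multiple deprivation (IMD" by decile) and, fourth, "classification of region (urban/rural").

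Protocol 10.4.1 sets out a multilevel linear model for the ABI total score. "Participants and PDU/JSWT will be fit as random effects", together with "pre-specified fixed effects for participant age, baseline IPV severity, and baseline ABI total score, and region". It gives no reason for leaving out the allocation factors and does not pass the choice of covariates to the statistical analysis plan.

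Protocol 10.4.2.1 carries the same approach to the continuous secondary outcomes. The record-linkage analysis in 10.7 does so for mortality, in logistic form.

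**The concern.** Minimising on a prognostic cluster factor evens it out between arms, so its variance no longer contributes to the true sampling variation of the treatment contrast. A model without that factor still counts the variance as between-cluster error. The reported standard error is then larger than the true one, the interval is too wide, and the test rejects less often than its nominal level. An analysis that includes the factor recovers the precision that the allocation paid for.

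The wording of *region* adds an ambiguity. Protocol 5.1 attaches the word to the urban/rural class, while 3.1 uses it for the geographical probation regions. On the first meaning the model omits three of the four allocation factors. On the second it omits all four and adjusts for something that was not balanced on. Two analysts could fit different primary models from the same sentence.

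**Working it through.** **Inputs from Protocol 10.3.** Standardised effect 0.4, two-sided 5%, 90% power, 26 clusters analysed, average size m = 13.5, ICC 0.03; 18% dropout; 32 clusters and 450 men enrolled.

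**Input not in the protocol.** R², the share of between-cluster variance that the minimisation factors explain. It is assumed, and shown from 0 upwards.

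**The plan's own figures.**
- Two-sample size with the t correction: 266, as stated.
- Design effect 1 + (13.5 − 1) × 0.03 = 1.375, and 266 × 1.375 = 366, against 358 stated (2.2% apart). Also 26 × 13.5 = 351.
- 358 / 0.82 = 437 against 450 enrolled; 26 / 0.82 = 31.7, hence 32 clusters; 32 × 14 = 448.

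The sample size reproduces closely. It takes no credit for any covariate.

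**Formulas** (K clusters, 1:1, SD = 1, allocation factors perfectly balanced):
- True variance of the contrast, which an adjusted model estimates: V_a = (4/K)[ICC(1 − R²) + (1 − ICC)/m].
- Variance estimated by a model that omits the factors: V_u = (4/K)[ICC + (1 − ICC)/m].
- Overstatement of the standard error: √(V_u/V_a) − 1.
- Type I error when omitted: 2[1 − Φ(1.96 √(V_u/V_a))].
- Power when omitted: Φ((0.4 − 1.96√V_u)/√V_a). Power when adjusted: Φ(0.4/√V_a − 1.96).

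**Numbers at K = 26.** (1 − 0.03)/13.5 = 0.07185. At R² = 0.5 the brackets are 0.03 + 0.07185 = 0.10185 and 0.015 + 0.07185 = 0.08685. √(0.10185/0.08685) = 1.083. The standard errors are √(4/26 × 0.10185) = 0.1252 and √(4/26 × 0.08685) = 0.1156.

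| R² | SE overstated | Type I, omitted | Power, omitted | Power, adjusted |
|---|---|---|---|---|
| 0 | 0% | 5.0% | 89.2% | 89.2% |
| 0.25 | 3.9% | 4.2% | 90.0% | 91.3% |
| 0.5 | 8.3% | 3.4% | 91.0% | 93.3% |
| 0.75 | 13.3% | 2.6% | 91.9% | 95.2% |
| 1 (ceiling) | 19.1% | 2.0% | 92.9% | 96.7% |

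**Allowing for cluster degrees of freedom.** The normal approximation hides the cost of extra cluster-level terms. Use t critical values on 26 − 2 = 24 degrees of freedom when omitted (2.064) and 26 − 2 − 4 = 20 when all four are added (2.086). Let the estimated variance follow V × χ²/df on those degrees of freedom. Power, omitted against adjusted, is then:
- R² = 0: 86.5% against 86.0%;
- R² = 0.25: 87.4% against 88.4%;
- R² = 0.5: 88.3% against 90.8%;
- R² = 0.75: 89.2% against 93.1%.

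**Simulation check.** Cluster means, constrained allocation, 26 clusters, 3,000 runs per case. Power omitted against adjusted was 86.5% against 86.0% (R² = 0), 86.5% against 87.4% (0.25), 88.5% against 90.6% (0.5) and 88.9% against 92.8% (0.75). Type I error with the factors omitted was 4.6%, 4.3%, 4.0% and 3.4%. The direction and approximate size agree.

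**All 32 clusters retained.** With 14 × 0.82 = 11.48 men each, the overstatement is 3.4%, 7.3% and 11.6% at R² = 0.25, 0.5 and 0.75.

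**Other ICCs (assumed).** At R² = 0.5 and K = 26 the overstatement is 3.1% for ICC 0.01 and 12.3% for ICC 0.05.

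**The case against.** The best defence is that nothing is lost against the plan. Protocol 10.3 claims no gain from covariates, so a model without the allocation factors has at least the power the calculation implies. Any loss is relative to a better model, the error is on the safe side, and if the factors are not prognostic, adjusting costs a little power. All of that stands.

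The model also already contains baseline ABI total, baseline IPV severity, age and some form of region. If these carry the differences between clusters, the R² that matters is what remains after them. It is smaller and unknown, and the figures above do not allow for it. A geographical region term could overlap with deprivation, ethnicity and urbanicity, and would use up cluster degrees of freedom of its own.

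The calculation assumes near-perfect balance. Protocol 3.1 describes 12 pilot clusters followed by 20 more, and staged allocation may balance less well. That would shrink the conservatism, although adjustment would still deal with the remaining imbalance.

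A detailed analysis plan is to be agreed before outcome data are assessed (Protocol 10). Estimation method and small-sample degrees of freedom are normal content for that document, so their absence from the protocol is no fault. The covariate list is different: 10.4.1 states it as pre-specified, so a plan that follows the protocol inherits the omission.

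**Conclusion.** The mismatch is real for ethnicity, unit size and deprivation, and unresolved for urban/rural class. Its consequence is conditional and modest, because cluster-level factors can only explain the between-cluster part of the variance, here 3%. For R² from 0 to 0.75 the standard error is overstated by 0% to 13%. Adjusting changes power by between a loss of up to about 1 point and a gain of 3 to 4 points. These figures assume near-perfect balance, equal cluster sizes, a single 12-month outcome, and no cluster variance already absorbed by the existing covariates; where some is absorbed, both effects are smaller.

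A reader might infer that all four factors are certainly omitted, or that the trial is certainly underpowered as a result. The protocol supports neither. The region term may be the urban/rural class, and no figure is given for how prognostic the factors are. The t-based power below 90% at 26 clusters is there at R² = 0 too, so it comes from the small number of clusters and not from the omitted covariates. There is no bias in the estimate and no excess of false positives.

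**What to change.** In Protocol 10.4.1, and in the analysis plan before outcome data are seen, add percentage non-white ethnicity, unit size, deprivation decile and urban/rural class as cluster-level fixed effects, continuous or linear where possible. Carry the same terms into the models that follow the primary one. State whether *region* is the urban/rural class or the geographical region. If it is the former, only three terms are new. If the sponsor prefers to leave any factor out, give the reason.

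The covariates are already held for randomisation, so no new data are needed. The cost is three to four cluster-level degrees of freedom out of 24 (26 clusters) or 30 (32 clusters), and up to about 1 point of power if the factors turn out not to be prognostic.
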